## **2. Objectives**

### **A. Primary**

1. To identify the most efficacious pressure of administration and minimum number of rubbing cycles necessary for STAR particles to penetrate the stratum corneum.

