### **B. STAR particle application**

A 1.5 gram dose of STAR particles (10% concentration in gel) will be applied to the eight application sites (forearm and hand) and 100 mg of the gel without STAR particles will be applied to the control site on one of the forearms. Two rubbing cycles (30 and 60 cycles at a minimum of 1 cycle/second) and three pressures (40, 60, and 80 kPa) will be evaluated. The parameters of each STAR particle application at each site (1-9) are labelled in Figure 1. The investigator will apply the STAR particles with two fingers (index and middle fingers of the dominant hand) and the pressure point of one finger is 1 cm^2. Pressures have been established with the following amount of STAR particles applied to the skin with one finger: 40 kPa (320 grams); 60 kPa (480 grams); and 80 kPa (640 grams). With two fingers, the investigator will apply with a pressure of 40 kPa when scale reads 640 grams; 60 kPa = 960 grams; and 80 kPa = 1280 grams. This will be practiced enough before the study so the investigator will know how much pressure generated on the skin based on previous practice with associating pressure according to scale weight.

[figure not shown]

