#### **Application of STAR particles to volar side of each forearm (Figure 1)**

1. Wash participant's arms and hands with disinfecting soap before any application.
2. Allowed skin to dry for at least 10 minutes.
3. Investigator to delimit the 9 areas on participant's forearms and hand with a marker.
4. Measure TEWL  $T_0$  on all 9 sites - measure from areas 1 to 9 and then from 9 to 1, giving 2 measurements for each time point according to Figure 1.
5. Apply STARS (80KPa for 60 cycles) on the dorsum of the closed hand.

6. Apply STARs (80KPa for 60 cycles) to the palmar surface of the same hand.
7. Apply STARs (pressure and # of cycles) to the six areas on the forearms per Figure 1.
8. Extra care will be taken to wash arms and hand with warm water to remove the STAR particles and gel and allowed to dry at least 5 min before the next TEWL ( $T_{20}$ ) is taken.
9. Measure TEWL  $T_{20}$  on all 9 sites - measure from areas 1 to 9 and then from 9 to 1, giving 2 measurements for each time point according to Figure 1.
10. Participant completes Tolerability Questionnaire
11. Participant completes Removal & Disposal Questionnaire and User's Feedback Questionnaire.
12. Pictures (3) will be taken to assess erythema: both forearms and the hand
13. Measure TEWL  $T_{30}$  on all 9 sites - measure from areas 1 to 9 and then from 9 to 1, giving 2 measurements for each time point according to Figure 1.
14. Apply GV staining for 10 minutes on the 2 arms resting with volar arm upward and right hand on a gauze containing GV stain.
15. Wash and wipe off the GV stain thoroughly with ethanol 70%.
16. Take 3 photos of each site to visualize the puncture after GV staining.
17. Using 2 fingers (index and middle), the participant will apply pressure to a kitchen scale in an effort to mimic application of low, medium, and high pressures.
18. The investigator records the weight (from the scale) when the pressure is constant.
19. Participant is discharged.

**Figure 1:** STAR particle application sites for V1 (participants #1-10)

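### Pressure is a primary factor, yet the protocol requires no check of the investigator's pressure at the visit, so drift or compression of the three levels would go unseen

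*Protocol*

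**What the plan says.** Protocol section 2.A sets the primary objective: "To identify the most efficacious pressure of administration and minimum number of rubbing cycles necessary" for the particles to penetrate the stratum corneum. Section 6.B states that "three pressures (40, 60, and 80 kPa) will be evaluated", together with 30 and 60 rubbing cycles at a rate with a floor of one cycle per second and no ceiling.

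On delivery, section 6.B says: "The investigator will apply the STAR particles with two fingers (index and middle fingers of the dominant hand"), with a contact area of 1 cm² per finger. Pressures are tied to scale weights, for one finger "40 kPa (320 grams); 60 kPa (480 grams); and 80 kPa (640 grams") and for two fingers 640, 960 and 1280 g. The control on what reaches the skin is: "This will be practiced enough before the study so the investigator will know how much pressure generated on the skin based on previous practice".

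The application steps (section 6.C, steps 5-7, for participants 1-10; section 6.D, steps 24-25, for participants 11-20) name pressures and cycles but no scale, sensor or recorded value. A scale appears only at the end of the visit, after gentian violet staining and photographs, when the participant presses it to mimic low, medium and high pressure: "The investigator records the weight (from the scale) when the pressure is constant" (step 18; the same at step 39). The schedule in section 9 lists this pressure test as its own row, apart from the application row.

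**The concern.** Pressure is one of the two factors the study exists to compare, and its levels are 20 kPa apart. The plan relies on an operator reproducing them from practised feel. It states no tolerance, no number of practice trials and no re-check. Practice comes before the study, while section 9 expects enrolment of all participants to take 3 months, and section 23 speaks of investigators in the plural. If the operator's sense of pressure shifts, or the three levels draw together, the protocol asks for nothing that would show it.

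The consequence falls on participants 1-10. Only they receive more than one pressure; participants 11-20 receive 80 kPa for 60 cycles. The interim analysis in section 5 may change pressure or rubbing cycles, so it would act on intended pressures that nobody has checked. If the first ten show a flat response, there would be no way to say whether pressure does not matter or was not delivered as planned.

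**Working it through.** **1. The protocol's own calibration.** Inputs from section 6.B: 1 cm² per finger; 320, 480 and 640 g for one finger; 640, 960 and 1280 g for two. Pressure = mass × 9.80665 m/s² ÷ area.

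- 320 g: 0.320 × 9.80665 = 3.138 N; over 0.0001 m² this is 31.4 kPa (label 40).
- 480 g: 47.1 kPa (label 60).
- 640 g: 62.8 kPa (label 80).

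Two fingers double both mass and area, so the results are the same. The labels are not reproduced: the weights give 31.4/40 = 0.785 of the stated pressure, about 22% less. A circular contact 1 cm in diameter (0.785 cm²) would give 39.96, 59.93 and 79.91 kPa. The ratio 1 : 1.5 : 2 holds either way, so this affects the absolute labels and not the intended order.

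**2. One pair of sites.** The protocol gives no repeatability, so the between-application CV is an assumption, taken from 5% to 30%. Model: delivered pressure is normal around its target *a* or *b*, with SD = CV × target and independent errors. The chance that the lower level is delivered harder than the higher is

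P = Φ(−(b − a) / (CV × √(a² + b²))).

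For 60 against 80 kPa, √(60² + 80²) = 100, so P = Φ(−0.20/CV). For 40 against 60 kPa, √(40² + 60²) = 72.1, so P = Φ(−0.277/CV).

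| Assumed CV | 60 above 80, per pair | 40 above 60, per pair |
|---|---|---|
| 5% | Φ(−4.00) ≈ 0% | ≈ 0% |
| 10% | Φ(−2.00) = 2.3% | 0.3% |
| 20% | Φ(−1.00) = 15.9% | 8.3% |
| 30% | Φ(−0.67) = 25.2% | 17.8% |

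The formula depends only on the ratio of the levels, so the conversion problem in step 1 does not alter these figures. They are per pair of sites. Three pressures by two cycle counts on six forearm sites suggests two such pairs per participant, but Figure 1 is not available to confirm the layout.

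**3. Averaged over participants 1-10.** The objective asks which level works best across participants. With one 60/80 pair each, the mean difference has SD CV × 100/√10 kPa, and the chance that mean delivered pressure reverses is Φ(−20 × √10/(100 × CV)):

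- CV 10%: Φ(−6.32) ≈ 0
- CV 20%: Φ(−3.16) = 0.08%
- CV 30%: Φ(−2.11) = 1.8%

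Independent error therefore seldom reverses the average order. It does add noise: the SD of the delivered 60/80 difference in one pair is 10, 20 or 30 kPa at CV 10, 20 or 30%, against an intended 20 kPa. Averaged over ten participants it is 3.2, 6.3 or 9.5 kPa.

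**4. Systematic error.** Suppose instead that every level is pulled towards 60 kPa, keeping only a fraction *c* of its intended distance. The delivered span from the 40 kPa site to the 80 kPa site is then 40*c* kPa in place of 40, and a linear response plotted against intended pressure has its slope multiplied by *c*. Averaging over more participants does not restore it. The protocol gives no basis for a value of *c*, and requires no data from which to estimate one.

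**The case against.** Delivery is not left to chance: section 6.B gives target weights for two fingers and requires practice against them. Each application has 30 or 60 cycles, so variation from stroke to stroke partly averages out. This is a declared pilot of 20 people with manual application and open treatment. Case report forms exist but are not shown, so a reading might be taken without the protocol asking for it. All of this stands. It limits the point to what the protocol requires, and it makes the matter an improvement in control and not a fatal flaw.

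The sentence linking 40 kPa to a scale reading of 640 g could, alone, suggest a live reading during rubbing. The sentence after it places the scale in earlier practice, and no procedure step puts a scale under a treated site.

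A reader might go further and infer that the three levels do overlap, that random error flattens the response, or that the ranking is likely to come out reversed. The protocol does not support any of these. Overlap is negligible at a CV of 5%, and the true CV is unknown. Error scattered independently around each target leaves the mean response by intended level roughly unbiased when the response is near linear. A shared proportional bias keeps the order. Flattening needs compression of the levels, and reversal needs drift that differs between them; the protocol neither shows these nor provides a way to exclude them. The lack of blinding is a declared design feature and adds nothing here.

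**Conclusion.** The point holds in a limited form. Pressure is a primary factor, the protocol controls it only by pre-study practice, and it requires no reading, tolerance or re-check of the investigator's pressure at the visit. Drift or compression could be neither detected nor excluded, and a flat pressure response in participants 1-10 could not be separated from poor delivery. No analysis can later recover a value that was never recorded.

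The chance of 60 kPa exceeding 80 kPa is about 0, 2, 16 or 25% per pair at an assumed CV of 5, 10, 20 or 30%. Across ten participants, the chance that independent error alone reverses the mean order is at most about 2%. These figures rest on the normal model, the assumed CV and one pair per participant. The main risks are added noise and unseen systematic drift, not a probable reversal. The mismatch between weights, contact area and kPa labels needs no assumption about repeatability, and these statements must be reconciled. The change is worth making, but the trial can run without it.

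**What to change.** 1. Reconcile the stated weights, the 1 cm² contact area and the kPa labels in section 6.B before any reading is used. Which of them changes is for the sponsor and investigator to decide.
2. With the scale already used at the visit, have the investigator press to each target weight immediately before the matching application, or at least at the start of each visit. Record the reading and the operator on the case report form, against a tolerance set in advance.
3. Report the operator's repeatability and any drift by pressure level, and make this available at the interim analysis after 10 participants.
4. State one cycle rate, or record the rate used, in place of a floor alone.

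The readings check calibration and drift. They do not measure pressure during rubbing and should not be analysed as if they did. The cost is a few minutes per visit and one case report form field per application, with no new equipment.

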### **C. Participants 1-10**

Enrolled healthy adults will receive eight applications (three on each forearm and two to one hand) of STAR particles and one control application on the volar side of one of the forearms for a total of nine applications to the forearms. In addition, two applications of STAR particles will be applied to one of the hands – one application to the palmar surface and one to the dorsum of the hand (Figure 1).

#### **Application of STAR particles to volar side of each forearm (Figure 1)**

1. Wash participant's arms and hands with disinfecting soap before any application.
2. Allowed skin to dry for at least 10 minutes.
3. Investigator to delimit the 9 areas on participant's forearms and hand with a marker.
4. Measure TEWL  $T_0$  on all 9 sites - measure from areas 1 to 9 and then from 9 to 1, giving 2 measurements for each time point according to Figure 1.
5. Apply STARS (80KPa for 60 cycles) on the dorsum of the closed hand.

6. Apply STARs (80KPa for 60 cycles) to the palmar surface of the same hand.
7. Apply STARs (pressure and # of cycles) to the six areas on the forearms per Figure 1.
8. Extra care will be taken to wash arms and hand with warm water to remove the STAR particles and gel and allowed to dry at least 5 min before the next TEWL ( $T_{20}$ ) is taken.
9. Measure TEWL  $T_{20}$  on all 9 sites - measure from areas 1 to 9 and then from 9 to 1, giving 2 measurements for each time point according to Figure 1.
10. Participant completes Tolerability Questionnaire
11. Participant completes Removal & Disposal Questionnaire and User's Feedback Questionnaire.
12. Pictures (3) will be taken to assess erythema: both forearms and the hand
13. Measure TEWL  $T_{30}$  on all 9 sites - measure from areas 1 to 9 and then from 9 to 1, giving 2 measurements for each time point according to Figure 1.
14. Apply GV staining for 10 minutes on the 2 arms resting with volar arm upward and right hand on a gauze containing GV stain.
15. Wash and wipe off the GV stain thoroughly with ethanol 70%.
16. Take 3 photos of each site to visualize the puncture after GV staining.
17. Using 2 fingers (index and middle), the participant will apply pressure to a kitchen scale in an effort to mimic application of low, medium, and high pressures.
18. The investigator records the weight (from the scale) when the pressure is constant.
19. Participant is discharged.

**Figure 1:** STAR particle application sites for V1 (participants #1-10)

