### 1. Study Summary

Project Title	Usability of STAR particles in healthy volunteers: A pilot study
Project Design	Non-randomized, controlled, non-blinded, single-arm pilot (feasibility) study, with an adaptative design at mid trial.
Primary Objective	To identify the most efficacious pressure of administration and the minimum number of rubbing cycles necessary to perforate the stratum corneum.
Secondary Objective(s)	To evaluate sensation and pain during and after STAR particle application.
Exploratory Objective(s)	To assess the dispersion and disposal of the STAR particles. To evaluate the user's feedback on product use.
Research Intervention(s)/Interactions	STAR particles STAR particles are millimeter-scale particles with micron-scale projections made of biocompatible materials that painlessly disrupt the stratum corneum. As STAR particles are rubbed on skin, their microscopic projections create micron-scale pores in the stratum corneum to increase skin permeability to topical compounds independent of physicochemical properties. After the arms of the STAR particle puncture the skin, the elastic forces of the skin push the particles out. Participants will receive the 8 interventions (different application pressures) plus the control (Site and treatment will not be randomly assigned on the arm) by the investigator.
Study Population	Adults (18 to 39 years of age)
Sample Size	20
Study Duration for individual participants	1 visit to screen for medical history, examine skin, obtain informed consent, and application of the STAR particles to the participant's forearm.
Study Specific Abbreviations/ Definitions	GV – Gentian Violet; kPa - kilopascal; microneedle (MN); TEWL – trans epidermal water loss; VAPS – visual analog pain scale
Funding Source (if any)	Aldena Therapeutics (United Kingdom)
Study Site	Emory Children's Center

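### In participants 1-10, the TEWL rounds give all sites the same mean reading time, but the forearm settings are applied one after another, so time since rubbing and gel contact differ between settings and are not recorded

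*Protocol*

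**What the plan says.** Section 6.B has a single operator: "The investigator will apply the STAR particles with two fingers (index and middle fingers of the dominant hand"). The conditions are "Two rubbing cycles (30 and 60 cycles at a minimum of 1 cycle/second) and three pressures (40, 60, and 80 kPa) will be evaluated".

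The step list in section 6.C sets the sequence for participants 1-10. Step 5 comes first: "Apply STARS (80KPa for 60 cycles) on the dorsum of the closed hand". Step 6 repeats that setting on the palm. Step 7 follows: "Apply STARs (pressure and # of cycles) to the six areas on the forearms per Figure 1". Step 8 is one wash of arms and hand, after which the skin is "allowed to dry at least 5 min before the next TEWL". Steps 4, 9 and 13 take TEWL at T0, T20 and T30, each time over all nine sites: "measure from areas 1 to 9 and then from 9 to 1, giving 2 measurements for each time point according to Figure 1".

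Section 1 adds that "Site and treatment will not be randomly assigned on the arm". Section 4.A makes TEWL at these time points part of the primary endpoint, together with the perforation count from gentian violet (GV) staining.

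No step records when rubbing ended at a site. No event is named from which 20 or 30 is counted. The gel-only control application has no step of its own in steps 5-7.

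**The concern.** The reading scheme treats the sites as if they had been treated at the same moment. They were not. The forearm area treated first has been perforated for longer, and has held gel for longer before the common wash, than the area treated last. TEWL after perforation may change as the skin recovers, so a difference between two settings could partly be a difference in elapsed time.

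The primary objective is to find the best pressure and the minimum number of cycles, and only participants 1-10 compare settings; participants 11-20 receive STAR particles at one setting. If the forearm order is the same for everyone, the lag runs in the same direction each time, and averaging over ten people does not remove it. Elapsed times that are not written down at the bedside cannot be recovered in the analysis.

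**Working it through.** **Inputs.** From the protocol: nine sites read forward and then backward (6.C); six forearm areas, three on each forearm (6.C); 30 or 60 cycles at no less than 1 cycle/s (6.B); one operator (6.B); one common wash (6.C, step 8). Assumptions: the six areas are the 3 pressures x 2 cycle counts (Figure 1 is not shown); readings are evenly spaced; changeover between areas takes 15-60 s; the rate is 1-2 cycles/s; the labels T20 and T30 are minutes.

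**1. Mean reading time.** In a round of 18 readings, site k is read at positions k and 19 - k. The mean is (k + 19 - k)/2 = 9.5 for every k. All sites therefore share one mean clock time, and so one mean time since the common wash. The scheme balances drift and drying, and leaves any difference in application time untouched.

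**2. Stagger among the six forearm areas.** Both hand sites receive 80 kPa and 60 cycles, so the comparison of settings rests on the forearm.
- Total forearm rubbing at 1 cycle/s: 3 x 30 + 3 x 60 = 270 s.
- End of first to end of last area: 270 - 60 = 210 s if a 60-cycle area comes first, or 270 - 30 = 240 s if a 30-cycle area does. That is 3.5-4.0 min, an upper bound for rubbing alone because 1 cycle/s is a minimum rate.
- At 2 cycles/s: 105-120 s, or 1.75-2.0 min.
- Five changeovers at 15-60 s: 75-300 s, or 1.25-5.0 min.
- Overall: 1.75 + 1.25 = 3.0 min to 4.0 + 5.0 = 9.0 min.

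Against a nominal 30 - 20 = 10 min between time points, this is about a third to nine-tenths of the gap.

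**3. What it could do to TEWL.** The protocol gives no recovery rate, so this is illustration only. If the rise in TEWL decayed exponentially with a half-life of 30 to 240 min, a lag of d min would change it by 1 - 2^(-d/half-life). For d = 4 min that is 8.8% down to 1.1%; for d = 9 min, 18.8% down to 2.6%.

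**4. Effect of reversing the order in alternate participants.** Let D be total forearm rubbing time, g a constant changeover, and d_j the rubbing time of area j. The end of rubbing at area j, summed over the forward and reversed orders, is D + d_j + 5g, so its mean is (D + d_j + 5g)/2. Two settings then differ by at most (60 - 30)/2 = 15 s at 1 cycle/s. If gel goes on as rubbing starts, the mean start is (D - d_j + 5g)/2, so gel-contact time also differs by at most 15 s.

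**The case against.** Much can be said on the other side, and it limits the point.

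- **Larger spread.** A reader might measure the stagger from the hand dorsum to the last forearm area, which gives 330 s of rubbing at 1 cycle/s and up to 12.5 min with 60 s changeovers. The hand sites carry one setting and differ from the forearm by anatomy, so they do not inform the comparison of settings. The forearm figure applies, and it stays below 10 min on the stated assumptions.
- **Drying.** A reader might infer that settings are read at different stages of drying. They are not, on average: the wash is common and mean reading time is equal. Only time since rubbing and gel contact differ.
- **Fixed order.** The text fixes dorsum, palm, then forearms. The order within the forearms depends on Figure 1, which is not shown, and the statement in section 1 about non-random assignment concerns which site gets which treatment. A lag always in one direction is therefore an inference. If the order is not fixed, the lag is instead uncontrolled and unrecorded.
- **Nine sites in sequence.** Steps 5-7 order eight STAR sites; the control has no stated place.
- **Wrong or overlapping time points.** A reader might say that T20 is not 20 minutes after application, or that the T20 round must run into T30. The protocol does not define the starting event or the reading time. An overrun of 10 min would need more than 600/18 = 33 s per reading, which is possible but not documented.
- **Importance.** This is a ten-person comparison within a pilot, no bias has been demonstrated, and the GV count is a separate part of the endpoint.

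Modelling elapsed time can be left to the analysis plan. Treatment order and time stamps cannot, and under a fixed order elapsed time would be nearly collinear with setting.

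**Conclusion.** The point holds as an inexpensive improvement to the TEWL part of the primary endpoint in participants 1-10. The 1-to-9-then-9-to-1 rounds equalise mean clock time but not time since rubbing or gel contact. Among the six forearm areas these differ by 3.5-4.0 min from rubbing alone at 1 cycle/s, and by about 3-9 min overall. This rests on a 3 x 2 layout, evenly spaced readings, 15-60 s changeovers and 1-2 cycles/s. Whether the lag always favours the same settings depends on Figure 1.

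The documents do not support the claim that TEWL differences between settings are mainly lag, because the size of the bias cannot be derived from them.

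**What to change.** - In step 7, treat the six forearm areas in the Figure 1 order in odd-numbered participants and in the reverse order in even-numbered ones. With equal changeovers this cuts the mean lag difference between settings from minutes to at most about 15 s at 1 cycle/s. It does not change which area receives which setting.
- Give the gel-only control application its own place in the sequence.
- Record the clock time at the end of rubbing at each site and at each TEWL reading.
- State the event from which T20 and T30 are counted, so that settings can be compared at a common elapsed time. Once the order alternates, elapsed time is no longer tied to setting and can be used in the analysis.
- Leave the questionnaires where they are. Moving them after T30 would delay the sensation and pain reports, which section 4.B places after each application.

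Cost: a simple order worksheet and extra time fields on the case report form. No added visits or staff are needed.

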#### **4. Study Endpoints**

##### **A. Primary**

- 1) For each primary objective, the **primary endpoint** is the identification of the most efficacious conditions measured by the number of perforations per cm^2 using GV staining and TEWL measurement before and after application of STAR particles [(T0 (before), T20 (after), T30, GV)].

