#### **5. Study Intervention/Investigational Agent**

This is a non-randomized, controlled, non-blinded, single-arm pilot study trial, with an adaptive design at mid-trial. After 10 participants complete the study, an interim analysis will be performed and recruitment will either continue with no change to the protocol or, changes may occur in regard to the STAR particle application area, position, pressure, or rubbing cycle in an adaptive design manner.

The trial will be performed in a climatized room and participants will have time to adapt and cool down to decrease risk of modulation TEWL reading.

The investigational agent will be STAR particles made of titanium dioxide, a widely used and safe ceramic material found in sunscreens, cosmetics, and paint. The star-shaped geometry is designed to inhibit complete insertion of the particle into skin, so STAR particles do not remain embedded in the skin. After the arms of the STAR particle puncture the skin, the elastic forces of the skin push the particles out. The STAR particles will be mixed with a gel formulation of the following composition: 0.7%w/w Xanthan Gum + 2.5%w/w Hydroxypropyl methylcellulose + Cyclomethicone and Dimethicone. STAR particles will be produced by Aldena Therapeutics under GMP conditions.

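### Participants 1-10: the minimum drying time after washing is 10 minutes before T0 but 5 minutes before T20, so wash water can raise the raw T0-to-T20 TEWL change

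*Protocol*

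**What the plan says.** The relevant steps are in Protocol Section 6.C (participants 1-10).

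- **Before T0.** Step 1: "Wash participant's arms and hands with disinfecting soap before any application". Step 2: "Allowed skin to dry for at least 10 minutes". Step 3 marks the nine areas, and step 4 takes T0.
- **Before T20.** Step 8: "Extra care will be taken to wash arms and hand with warm water to remove the STAR particles and gel", after which the skin is "allowed to dry at least 5 min before the next TEWL". Step 9 takes T20.
- **Reading order.** Each TEWL round (T0, T20, T30) goes through the sites from 1 to 9 and back from 9 to 1, so each site is read twice.
- **Endpoint.** Section 4.A bases the primary endpoint on perforations per cm², "using GV staining and TEWL measurement before and after application of STAR particles", and names T0, T20 and T30.
- **Control.** Section 6.B: "100 mg of the gel without STAR particles will be applied to the control site on one of the forearms". The hand has two STAR sites and no gel-only site.
- **Measurement conditions.** Section 5 uses a climatized room, and "participants will have time to adapt and cool down to decrease risk of modulation TEWL reading".

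**The concern.** TEWL records water leaving the skin surface, and water left by a wash adds to the reading until it has gone. A before-after comparison is clean only if both readings follow the same preparation. Here the second reading may come after half the drying time of the first, and after a warm-water wash. Section 5 shows that the protocol wants to avoid disturbed TEWL readings, but it states no renewed adaptation period after step 8 and no correction for the shorter interval.

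What is at stake is the raw T0-to-T20 change at each site. If part of it is wash water, the size of the barrier change at T20 is overstated. This matters most at the two hand sites, where no gel-only site on the hand shows what the wash alone does.

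**Working it through.** The protocol gives no figure for residual water, so there is nothing to reproduce. The check compares the two intervals and then illustrates direction and scale.

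**Inputs from the protocol (Section 6.C).** Minimum drying before T0: 10 minutes (step 2). Minimum drying before T20: 5 minutes (step 8). Ratio: 5/10 = 0.5.

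**Assumptions not in the protocol.** The excess reading just after a wash is E, the same after both washes, and it decays exponentially with half-life h minutes.

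**Spurious change at the minima.** Excess at T0 = E × 2^(−10/h). Excess at T20 = E × 2^(−5/h). Spurious T0-to-T20 change = E × (2^(−5/h) − 2^(−10/h)).

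| h (min) | Excess at T20 | Excess at T0 | Ratio | Spurious change |
|---|---|---|---|---|
| 2 | 0.177E | 0.031E | 5.7 | 0.15E |
| 5 | 0.500E | 0.250E | 2.0 | 0.25E |
| 10 | 0.707E | 0.500E | 1.4 | 0.21E |

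Under these assumptions the change is upward for every h. With equal minima it is zero.

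**How far the direction depends on equal wetness.** The washes differ: disinfecting soap before T0, warm water before T20. If the starting excess before T20 is a fraction r of that before T0, the spurious change is zero when r × 2^(−5/h) = 2^(−10/h), so r = 2^(−5/h). That is 0.18, 0.50 or 0.71 for h = 2, 5 or 10. Below that fraction the sign reverses.

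**Cancellation between sites.** An excess common to all sites drops out of any contrast between them. The 1-to-9, 9-to-1 order gives every site the same mean position, which removes a linear drift but not all of a decaying one. Assume 1 minute per reading and h = 5. Site 1 is read at minutes 0 and 17 of the round, site 9 at minutes 8 and 9. As a fraction of the excess at the start of the round:

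- Site 1: (1 + 2^(−17/5))/2 = (1 + 0.095)/2 = 0.55
- Site 9: (2^(−8/5) + 2^(−9/5))/2 = (0.330 + 0.287)/2 = 0.31

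The difference in round-start excess between T20 and T0 is 0.25E, so the change scores carry 0.55 × 0.25E = 0.14E at site 1 and 0.31 × 0.25E = 0.08E at site 9. The spurious contrast between these two sites is about 0.06E, against 0.25E for a reading at the start of each round.

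**The case against.** The strongest reply is that the primary objective asks which pressure and number of cycles work best, not whether STAR particles raise TEWL. That is a comparison of forearm sites within a person, washed together and read in one round, so a shared excess largely cancels. This stands. A reader might infer that the choice of pressure or cycles is compromised, but the documents do not show that. Only a partial remainder from a decaying excess survives, and its size is unknown.

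Other points also stand:

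- Both intervals are minima. Actual times could be equal or even reversed. However, a compliant visit may use 5 minutes before T20, and marking the nine areas adds time before T0.
- The gel-only control is on a washed forearm and is read at T20, so it shows the effect of the wash there.
- T30 follows the T20 round, the questionnaires and the photographs, so drying is longer. GV counts do not depend on drying. T20 is therefore only one part of the primary endpoint.
- Both hand sites receive one fixed condition, so they do not inform the choice among pressures and cycles. Their raw change is still harder to interpret without a hand control.
- How the TEWL change is analysed may be set out in a SAP that is not at hand. The lack of a control-adjusted definition in the protocol is not itself a fault.

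A reader might also infer that a fall from T20 to T30 would be misread as barrier recovery. Recovery is not among the objectives or endpoints in Sections 2 and 4, so no stated aim depends on it.

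**Conclusion.** The asymmetry is in the text and unexplained: at least 10 minutes of drying before T0 and at least 5 before T20, for participants 1-10. At these minima, leftover wash water can raise the raw T0-to-T20 change. The illustrative rise of 0.15E to 0.25E rests on assumed half-lives and equal starting wetness. E in TEWL units is not in the document and could be negligible.

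It is tempting to read this as a certain bias in one direction, toward a STAR effect. The documents do not support that. The intervals are minima, the washes differ in kind, and nothing shows that water remains after 5 minutes. The effect largely cancels between forearm sites and against the gel control, T30 is less affected, and GV counts are unaffected. Participants 11-20 are outside the point: under Section 6.D the gel is removed dry and no T20 step is listed. This is a minor, avoidable flaw in measurement procedure.

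**What to change.** In Section 6.C, step 8, set the same minimum drying time before T20 as step 2 sets before T0. As a supporting measure, interpret the forearm TEWL change from T0 relative to the change at the concurrent gel-only control site. This belongs in the SAP if it is not already there. It does not cover the hand sites, for which equal drying is the main protection.

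The cost is about 5 minutes in a visit of roughly two hours. The first post-application reading, and possibly T30, would fall about 5 minutes later. The protocol does not define the T20 and T30 labels. If they are minutes, they should be checked against the new timing.
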